5.1.2. Secondary Endpoints

The percentage of subjects with a change in intended prostate cancer treatment plans due to ¹⁸F-DCFPyL PET/CT as measured by comparison of intended management questionnaires completed Pre- and Post- ¹⁸F-DCFPyL PET/CT imaging results (based on local reader interpretation) (see Section 8.5.3).

The endpoint is the percentage of subjects with a change in intended prostate cancer treatment plan from Pre- and Post ¹⁸F-DCFPyL PET/CT scan assessed using the MMQ, based on local ¹⁸F-DCFPyL PET/CT scan read results, as the decision to change the subject's treatment plan or not to change plans is made using this data.

Any change in planned management, whether from no treatment to any treatment, from one treatment to another between treatment categories or within a treatment category will be tabulated as a change. Change vs. no change will be analyzed as a binary response.

The shifts between no planned treatment and the major categories of planned therapy as well as between those categories are defined in Table 5.

Table 5: Changes in Planned Therapy

Pre- ¹⁸ F-DCFPyL PET/CT scan	Post- ¹⁸ F-DCFPyL PET/CT scan
No treatment planned	Any treatment planned
Any treatment planned	No treatment planned
Treatment planned - local therapy	Treatment planned - systemic therapy
Treatment planned - systemic therapy	Treatment planned - local therapy
Treatment planned - local therapy	Treatment planned - other therapy
Treatment planned – systemic therapy	Treatment planned - other therapy
Treatment planned – other therapy	Treatment planned – systemic therapy
Treatment planned – other therapy	Treatment planned – local therapy

5.1.3. Tertiary/Exploratory Endpoints

• Detection Rates by Anatomic Region

The detection rate is defined as the percent of positive ¹⁸F-DCFPyL PET/CT scans identified by the central imaging readers. It is calculated as the number of subjects with positive scans divided by the number of subjects who have evaluable scan results reported times 100. For this analysis, if a subject has a PyL positive scan in any of the anatomic regions defined in Table 3: prostatic, pelvic, extra-pelvic lymph nodes, extra-pelvic bone and extra-pelvic other, then the subject will be counted within the respective region. Another tabulation will assess detection rates in the prostatic, pelvic and extra-pelvic regions, where all extra-pelvic regions (lymph node, bone and other tissue) will be combined. If a subject has lesions detected in more than one anatomic region, then that subject will be counted for all respective regions.

• PPV by Anatomic Region

The PPV for subjects with positive ¹⁸F-DCFPyL PET/CT scans is defined as the percent of subjects with true positive results divided by all subjects with ¹⁸F-DCFPyL PET/CT scans or TP/(TP+FP)00%. For this analysis, the subject will be designated as a TP if the ¹⁸F-DCFPyL PET/CT scan identified by the central imaging readers has at least one lesion and the respective truth standard result has a positive finding in the respective regions as defined in Table 3: prostatic, pelvic, extra-pelvic lymph nodes, extra-pelvic bone and extra-pelvic other. Another tabulation will assess PPV in the prostatic, pelvic and extra-pelvic regions, where all extra-pelvic regions (lymph node, bone and other tissue) will be combined. If a subject has lesions detected in more than one anatomic region, then that subject's results will be included in all respective regions.

• False Positive Scan Rates

Subjects with false positive scans are defined as subjects with positive ¹⁸F-DCFPyL PET/CT scans identified by a central reader who do not have confirmation of any lesions by a truth standard. The false positive rate is calculated as the number of subjects with positive scans defined by the central imaging reader without confirmation by any truth standard, divided by the number of subjects who have positive scan results times 100.

• Detection Rates by Baseline PSA

In addition to presenting detection rates by anatomic region of the lesions, detection rates of any PyL positive lesion at the subject level identified by the central imaging readers will be summarized for all subjects grouped by baseline PSA values categorized as: $< 0.2 \text{ ng/mL}, 0.2 \text{ to} < 0.5 \text{ ng/mL}, 0.5 \text{ to} < 1 \text{ ng/mL}, 1 \text{ to} < 2 \text{ ng/mL}, 2 \text{ to} < 5 \text{ ng/mL} \text{ and} \ge 5 \text{ ng/mL}.$

• False Negative and True Negative Subjects

Subjects may have a positive PyL scan by local interpretation and available truth standard data, but the central readers identify the scan as negative. If this situation arises, the following rules will apply:

• If the central reader classifies the scan as negative and the truth standard is positive, then the subject will be considered a false negative

• If the central reader classifies the scan as negative and the truth standard is negative, then the subject will be considered a true negative

• True Positive Detection Rate

The overall true positive detection rate (TPR) is the rate of subjects with positive ¹⁸F-DCFPyL PET/CT scans identified by a central reader confirmed to have a positive SOT (ie, a true positive [TP] subject) divided by the total number of subjects who had a ¹⁸F-DCFPyL PET/CT scan interpreted by a central reader times 100. This represents the total fraction of true positive subjects, or TP/ (TP+FP+TN+FN), where the sum of negative PyL scans (TN+FN) are reported even if the specific breakdown of TN and FN numbers may be unknown.

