10.4.2. Efficacy Analyses

Efficacy endpoints will be assessed using the FAS. Continuous monitoring will be performed with respect to the number of subjects evaluable for the primary endpoint. When the required number of subjects with positive ¹⁸F-DCFPyL PET/CT scans and information for the composite truth standard are available for calculation of the CLR, subject enrollment and follow-up assessments will conclude, and the study database will be locked for analysis. Any subjects who are undergoing efficacy evaluations who have not contributed endpoint data at the time of database lock will be censored and will be treated as unevaluable for efficacy.

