• PSA decreases by ≥50% from baseline following RT (without concomitant ADT) up to nine months following initiation of such treatment if the other two truth standards were not performed or did not provide evaluable results

False positives will be defined as subjects with positive lesion(s) on PyL PET/CT from at least one central reader who has the following negative findings for prostate cancer according to the composite truth standard:

- Negative finding for prostate cancer of a PyL-suspected lesion according to local histopathology, or
- Negative finding for all PyL positive lesion(s) upon follow-up correlative imaging performed following PyL PET/CT, or
- PSA does not decrease by ≥50% from baseline following RT (without concomitant ADT) up to 9 months following initiation of such treatment.

The CLR lesion location(s) will be matched with the CLR lesion location(s) identified by the composite truth standard to determine if colocalization is successful, denoting a true positive (TP) assessment. If a subject has more than one lesion identified by pathology or by correlative imaging, then at least one lesion must be successfully colocalized for the subject to be considered a TP. The anatomic regions and CLR lesion locations matched by laterality (right or left) where applicable are presented in Table 3. The pelvic lymph nodes are grouped together for analysis in alignment with the data collected in the PyL-2301 (OSPREY) study. Within the prostatic region and extra-pelvic lymph nodes, specific CLR lesion location groupings are further modified specific for PET/CT findings based on Prostate Cancer Molecular Imaging Standardized Evaluation (PROMISE)² intended to guide reproducibility, general applicability and clinical relevance.

Table 3: Lesion Locations and Anatomic Regions

Anatomic Region	CLR Lesion Locations
Prostatic	Prostate gland or prostate bed (including seminal vesicles)
Pelvic Lymph Nodes	 Right Pelvic (including Internal Iliac [Hypogastric], External Iliac, Common Iliac, Obturator) Left Pelvic (including Internal Iliac [Hypogastric], External Iliac, Common Iliac, Obturator) Other pelvic (including Rectal/perirectal and Presacral)

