Extra-pelvic (Lymph Nodes)	 Retroperitoneal (including Para/Peri-Aortic R/L and Celiac axis R/L) Supradiaphragmatic (including Supraclavicular R/L, Pre/Paratracheal R/L, Posterior Mediastinal R/L, Anterior Mediastinal R/L, Subcarinal, Paracardiac R/L, Retrocrural R/L, Thoracic Hilar R/L, Mesenteric R/L, Axillary R/L, Cervical R/L)

Statistical Analysis Plan: Protocol PyL3301

Anatomic Region	CLR Lesion Locations
	Other extra-pelvic (specify, including Inguinal/Femoral R/L)
Extra-pelvic (Bone)	 Pelvic bone R/L Skull Clavicle R/L Scapula R/L Sternum Ribcage R/L Spine (including cervical/thoracic/lumbar/sacral) Extremities (including right upper, right lower, left upper, left lower) Other bone lesion
Extra-pelvic (Visceral/soft- tissue)	 Lung/pleura Liver Other visceral/soft tissue lesion (including spleen, adrenal, mediastinum, pericardium, non-nodal retroperitoneal tissue, and other visceral/soft-tissue)

Each subject will be evaluated for the primary endpoint using a single truth standard source. If a subject has more than one source, e.g., undergoes correlative imaging and needle-guided biopsy, the pathology result from the needle biopsy will be evaluated as the truth standard. If the pathology result is unevaluable or the biopsy needle is not in a positive PyL lesion, then the results of the correlative imaging will be used as the truth standard.

Subjects with positive ¹⁸F-DCFPyL PET/CT scans per local scan interpretation (detection of disease at any location) will be followed at the Efficacy visit(s) based on their ¹⁸F-DCFPyL PET/CT finding(s) (see Section 4). If a subject has a negative ¹⁸F-DCFPyL scan by the local interpretation, then no standard of truth data will be submitted by the study site and no efficacy evaluation will be performed by the central Truth Panel readers. If the subject's ¹⁸F-DCFPyL PET/CT scan is interpreted as positive by one or more of the central readers and no standard of truth data is available for evaluation, then the subject will be considered unevaluable for the primary endpoint. Please see Section 5.1.3 for subjects with positive ¹⁸F-DCFPyL scans by local interpretation where the central reader(s) identify the scan as negative.

Subjects with positive ¹⁸F-DCFPyL PET/CT scans (by central review) will be classified as TP, FP or unevaluable as presented in Table 4.

Table 4: Primary Endpoint Assessment

Composite Truth Standard Source	Truth Standard Location Result	Central PyL Reader Location Match	Subject Outcome

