8.4. Missing Efficacy Endpoints

Missing values will not be replaced for any endpoint. There should be no missing primary endpoint values for subjects with evaluable PyL scans as assessed by the central readers unless no follow-up standard of truth (SOT) was completed. The subjects will be classified as true positive, false positive, or unevaluable. If a subject undergoes PyL imaging and does not have any follow-up evaluations or if the follow-up assessments are deemed unevaluable by the central readers based on image quality or other reasons, then that subject will be considered as unevaluable.

Exploratory evaluations of the primary endpoint will be performed using multiple imputation methods to examine the impact of missing or unevaluable SOTs for subjects with positive PyL scans as interpreted by the central readers. These methods are described in detail in section 8.5.2.2.

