8.5.4. Analysis of Exploratory Efficacy Endpoints

Exploratory efficacy endpoints will be generated using the FAS to calculate detection rates on the subset of the FAS with at least one positive lesion identified by PyL PET/CT imaging for PPV and false positive scan rate endpoints. If a subject has more than one truth standard modality, (i.e., an image-guided biopsy and a correlative imaging scan) the information from the modality(ies) not used for the primary endpoint will be utilized in the calculation of exploratory endpoints. As there are results reported for three independent readers, these summary tables will present the respective endpoints for each reader.

The following endpoints will be analyzed using a two-sided 95% CI presented for each central imaging reviewer and for the local site interpretation separately based on a normal approximation to the binomial:

- Detection rates of ¹⁸F-DCFPyL PET/CT imaging by lesions in the following regions: prostatic, pelvic, extra-pelvic lymph nodes, extra-pelvic bone and extra-pelvic other defined in Table 3 in Section 8.5.2.1
- Detection rates of ¹⁸F-DCFPyL PET/CT imaging by lesions in the following regions: prostatic, pelvic, extra-pelvic (lymph nodes, bone and other combined) defined in Table 3 in Section 8.5.2.1
- The detection rates of ¹⁸F-DCFPyL PET/CT imaging as a function of baseline PSA groups categorized as <0.2 ng/mL, 0.2-< 0.5 ng/mL, 0.5-<1 ng/mL, 1-<2 ng/mL, 2-<5 ng/mL, ≥5 ng/mL

- Detection rates of ¹⁸F-DCFPyL PET/CT imaging by baseline Screening imaging modality, categorized as fluciclovine PET/CT, choline PET, NaF PET, Pelvic CT or MRI, Abdomen CT or MRI, Chest CT or MRI, bone scintigraphy
- The percentage of subjects with positive ¹⁸F-DCFPyL PET/CT scans assessed by the central reader who have negative findings for prostate cancer (false positive subjects) based on the composite truth standard. The percentage of false positive scans is defined as (1-CLR).
- The PPV of ¹⁸F-DCFPyL PET/CT for prostatic, pelvic, extra-pelvic lymph nodes, extra-pelvic bone and extra-pelvic other regions defined in Table 3 in Section 8.5.2.1, based on the composite truth standard in subjects with positive lesion(s) on ¹⁸F-DCFPyL PET/CT imaging
- The PPV of ¹⁸F-DCFPyL PET/CT for prostatic, pelvic and extra-pelvic (lymph nodes, bone and other combined) regions defined in Table 3 in Section 8.5.2.1, based on the composite truth standard in subjects with positive lesion(s) on ¹⁸F-DCFPyL PET/CT imaging

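### Two exploratory SAP rates, false positive and true positive detection, each have two conflicting definitions for centrally positive subjects without evaluable truth data

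*SAP*

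**What the plan says.** **False positive rate.** SAP 5.1.3 takes as numerator every subject whom a central reader calls positive and who lacks confirmation, over all subjects with positive scans: "the number of subjects with positive scans defined by the central imaging reader without confirmation by any truth standard, divided by the number" of such subjects. SAP 8.5.4 ties the same endpoint to negative findings on the composite truth standard and adds: "The percentage of false positive scans is defined as (1-CLR"). Protocol 10.4.2.3 gives the same rule. SAP 8.5.2.1 computes CLR as TP/(TP+FP) over evaluable subjects only.

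**What counts as FP.** SAP 5.1.1 reserves FP for a centrally positive subject "who has the following negative findings for prostate cancer according to the composite truth standard". A central positive without truth data is placed elsewhere: "then the subject will be considered unevaluable for the primary endpoint". SAP 8.4 confirms three classes: "The subjects will be classified as true positive, false positive, or unevaluable".

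**True positive detection rate.** The wording in SAP 5.1.3 divides true positives by all subjects whose scan a central reader interpreted. The formula given with it is TP/(TP+FP+TN+FN). It keeps all negative scans, even those that cannot be split into TN and FN, and has no term for unevaluable positives. SAP 8.5.4 puts this rate on the primary endpoint table.

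**Extra truth sources.** SAP 5.1.1 gives each subject one truth source for the CLR. SAP 8.5.4 says that information from modalities "not used for the primary endpoint will be utilized in the calculation of exploratory endpoints".

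**The concern.** Followed as written, the SAP yields two values for each rate as soon as one centrally positive subject has no evaluable truth standard. Under the 5.1.3 false positive definition, a man who was never verified is reported as a false positive. Under the detection rate formula, unverified positives leave the denominator while unverified negatives stay in, which raises the rate.

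Such subjects arise by design:

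- If the local read is negative, "no standard of truth data will be submitted by the study site and no efficacy evaluation will be performed", so a central positive in that man cannot be verified (SAP 5.1.1).
- Subjects without evaluable histopathology or informative imaging who do not start radiotherapy alone within 60 days are discontinued (Protocol 4.1).
- Table 4 of the SAP ends in an unevaluable outcome for an unconfirmed PSA response and for radiotherapy that did not cover all suspected lesions.
- Subjects still in follow-up at database lock "will be censored and will be treated as unevaluable for efficacy" (Protocol 10.4.2).

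Neither rate has a success criterion. But one is a protocol-listed exploratory endpoint and the other will be printed beside the CLR. Choosing between definitions once the data are known would be a post hoc choice.

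**Working it through.** **Inputs (SAP 7.1):** CLR 30%, positive scan rate 60%, non-evaluable rate 30%, 192 subjects scanned, lower 95% confidence bound for CLR 20%.

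**The plan's own figures reproduce.**

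- Evaluable positives: 1.96² × 0.3 × 0.7 / 0.1² = 80.67, rounded up to 81.
- Scans: 80.67/0.6 = 134.5 (stated as 134).
- Allowing for 30% non-evaluable: 134/0.7 = 191.4, so 192.

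**Assumption.** The plan does not split the 30% non-evaluable rate by scan result; it is applied here to positive scans. This agrees with the plan's chain: 192 × 0.6 × 0.7 = 80.6, in line with the 81 required.

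**Notation.** P = 192 × 0.6 = 115.2 positives; 76.8 negatives; u = unevaluable share of positives; c = CLR. Then TP = c(1-u)P, FP = (1-c)(1-u)P and U = uP.

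**Formulas**

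- False positive rate, SAP 5.1.3 read literally: (FP+U)/(TP+FP+U) = 1 - c(1-u)
- False positive rate, SAP 8.5.4: FP/(TP+FP) = 1 - c
- Detection rate, wording: TP/192 = 0.6c(1-u)
- Detection rate, formula: TP/(TP+FP+76.8) = 0.6c(1-u)/[0.6(1-u)+0.4]

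**Planning case, c = 0.3 and u = 0.3.** TP = 24.2, FP = 56.4, U = 34.6.

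- False positive rate: (56.4+34.6)/115.2 = 79.0%, against 56.4/80.6 = 70.0%.
- Detection rate: 24.2/192 = 12.6%, against 24.2/(80.6+76.8) = 15.4%.

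**Range over u at c = 0.3**

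| Unevaluable share of positives | FP rate, 5.1.3 | FP rate, 1-CLR | Detection rate, wording | Detection rate, formula |
|---|---|---|---|---|
| 0% | 70.0% | 70.0% | 18.0% | 18.0% |
| 10% | 73.0% | 70.0% | 16.2% | 17.2% |
| 20% | 76.0% | 70.0% | 14.4% | 16.4% |
| 30% | 79.0% | 70.0% | 12.6% | 15.4% |
| 40% | 82.0% | 70.0% | 10.8% | 14.2% |

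The gap in the false positive rate is [1 - c(1-u)] - (1-c) = cu, so it grows with the CLR. At c = 0.8 and u = 0.3 (0.8 is illustrative, not a plan figure) the rates are 44.0% against 20.0%, and the detection rates 33.6% against 41.0%.

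**A second source of divergence.** Take a subject whose biopsy of the suspected lesion is negative but whose correlative imaging is positive at a matching site. The CLR uses the biopsy, so he is FP. Under 5.1.3 any truth standard suffices, so he is confirmed. The false positive rate then differs from 1-CLR even if nobody is unevaluable. The documents give no figure for how often this would happen.

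**The case against.** **There may be one root question, not two.** If unconfirmed positives counted as FP throughout 5.1.3, TP+FP would be all positives and the detection rate formula would match its wording. The link is real. But TP and FP in that formula are outcome classes defined in 5.1.1 and Table 4, where FP needs a negative truth finding or a location mismatch and unevaluable is separate. The statements on unevaluable subjects in 5.1.1 and 8.4 do concern the primary endpoint, but no other definition of these classes is given for the detection rate.

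**1-CLR is already explicit in two places, and 5.1.3 could be read benignly.** One could take lack of confirmation to mean a negative test, and positive scans to mean evaluable ones. That would restore 1-CLR, and it shows which definition to keep. But the text does not say so, and no rule of precedence is stated.

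**The 30% CLR may already treat unverified positives as unconfirmed.** SAP 7.1 multiplies 60% by 30% to reach 18% of the population, as if 30% were a share of all positives. On that reading, with u = 0.3, TP = 0.3P and FP = 0.7P - 0.3P = 0.4P. The false positive rates become (0.4+0.3)/1 = 70.0% against 0.4/0.7 = 57.1%. The detection rates become 0.6 × 0.3 = 18.0% against 0.18/(0.42+0.40) = 22.0%. The levels move, but the gaps remain.

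**Both rates are exploratory.** This stands, and it limits the weight of the point.

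**Conclusion.** The inconsistency is real for both rates. For the false positive rate, 5.1.3 is the outlier: it conflicts with 8.5.4, with Protocol 10.4.2.3 and with the SAP's own FP class. It also conflicts in spirit with SAP 8.5.2.2, which imputes missing truth results for these subjects and so treats them as unknown, not false. For the detection rate, the wording should govern, since keeping unsplit negatives shows that the intended base is every scan read.

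In the planning case the discrepancy is 9 percentage points for the false positive rate and 2.8 for the detection rate (15.4% less 12.6%). These sizes depend on the assumed unevaluable share and on reading the 30% CLR as a rate among evaluable positives. That the definitions differ whenever a central positive is unevaluable depends on neither.

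The CLR, its two-of-three-reader success rule and the sample size are untouched. The point should be corrected because, as written, the SAP can report unverified men as false positives and overstate a rate shown on the primary endpoint table.

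The last bullet of SAP 8.5.4 is only a drafting slip. It opens with a base of positive scans, then includes both positive and negative findings and defers to 5.1.3.

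**What to change.** Amend the SAP before database lock:

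1. **5.1.3, false positive rate:** define it as FP/(TP+FP) = 1-CLR, using the single truth source assigned for the primary endpoint. State in 8.5.4 that the use of additional truth modalities does not apply to this rate; otherwise it cannot equal 1-CLR.
2. **5.1.3, detection rate:** change the formula to TP/(TP + FP + unevaluable positives + all negatives), so that it agrees with its wording.
3. **8.5.4, last bullet:** delete the first occurrence of the word *positive*, so that the base is all subjects with a centrally read scan.
4. **Primary endpoint table:** for each reader, show the number of unevaluable centrally positive subjects on a separate line.

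The cost is a few wording changes and one table line. No new data are needed and the primary analysis does not change. The detection rate becomes somewhat less favourable than under the present formula.

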5. SUBJECT SELECTION AND WITHDRAWAL CRITERIA

5.1. Subject Inclusion Criteria

Subjects must meet all of the following inclusion criteria:

1. Male \geq 18 years of age
2. Histopathologically confirmed prostate adenocarcinoma per original diagnosis, with subsequent definitive therapy
3. Suspected recurrence of prostate cancer based on rising PSA after definitive therapy on the basis of:
 - a. Post-radical prostatectomy (RP): Detectable or rising PSA that is \geq 0.2 ng/mL with a confirmatory PSA \geq 0.2 ng/mL (American Urological Association [AUA] recommendation)³⁹; or
 - b. Post-radiation therapy (RT), cryotherapy, or brachytherapy: Increase in PSA level that is elevated by \geq 2 ng/mL above the nadir (American Society for Therapeutic Radiology and Oncology [ASTRO]-Phoenix consensus definition)⁴⁰
4. Negative or equivocal findings for prostate cancer on conventional imaging performed as part of standard of care workup within 60 days prior to Day 1
5. Life expectancy \geq 6 months as determined by the investigator
6. Able and willing to provide informed consent and comply with protocol requirements

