8.5.2.2. Sensitivity Analyses of the Primary Endpoint

The primary endpoint analysis will be repeated for subjects in the per-protocol analysis set, which excludes subjects with major protocol deviations.

There will also be an analysis of the primary endpoint for subjects who have positive ¹⁸F-DCFPyL scans as reported by local interpretation. These subjects will have their endpoint evaluated following the same criteria as described in Table 3. The CLR and its corresponding 95% confidence interval will be calculated in the same manner as for the three independent central PyL readers. If there are more subjects with positive PyL scans identified by the central readers than those identified by the local readers, then a population of subjects with positive scans by local read results may be used.

There will be an analysis of the primary endpoint in the full analysis set with positive ¹⁸F-DCFPyL PET/CT imaging as assessed by the central imaging readers, where the CLR lesion location recorded for pelvic lymph nodes will be grouped according to the PROMISE - standardized lymph node template² (internal iliac left, internal iliac right, external iliac left, internal iliac right, obturator left, obturator right, common iliac left, common iliac right, presacral and other pelvic lymph nodes). All other CLR lesion locations will be assessed, including laterality where applicable, as described in Table 3.

There will be an analysis of the primary endpoint in the full analysis set with positive ¹⁸F-DCFPyL PET/CT imaging as assessed by the central imaging readers, where the specific lesion location recorded on the case report form, including laterality where applicable, is used instead of the CLR lesion location as described in Table 3.

A summary table will present the number and percent of subjects with either false negative or true negative outcomes for each central imaging reader. A data listing of subjects in these endpoint categories will also be prepared.

As noted in section 8.4, pattern mixture model-based multiple imputations (MI) assuming data are missing-at-random (MAR) and tipping point analyses will be performed as sensitivity analyses to examine the influence of the missing or unevaluable SOTs for subjects who have ¹⁸F-DCFPyL PET/CT results reported by a central reader. ¹⁰ The locations of lesions as identified by the central reader(s) will be imputed as the lesion locations in the multiple imputation scenarios.

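### SAP 5.1.3 calls a man a true negative when the evidence shows only that a locally suspected lesion was not confirmed, or that PSA did not halve after radiotherapy

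*SAP*

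**What the plan says.** SAP 5.1.3 provides for disagreement between the local and central reads: "Subjects may have a positive PyL scan by local interpretation and available truth standard data, but the central readers identify the scan as negative". If the truth standard is positive in such a man, he is a false negative. Otherwise: "If the central reader classifies the scan as negative and the truth standard is negative, then the subject will be considered a true negative". The label attaches to the subject, and the rule makes no distinction by source of truth.

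Section 5.1.3 does not define a negative truth standard, and Table 4 in SAP 5.1.1 classifies centrally positive scans only. The meaning has to come from the false-positive definition in SAP 5.1.1, which covers a subject "who has the following negative findings for prostate cancer according to the composite truth standard" and lists three routes:

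- Histopathology: "Negative finding for prostate cancer of a PyL-suspected lesion according to local histopathology".
- Correlative imaging: "Negative finding for all PyL positive lesion(s) upon follow-up correlative imaging performed following PyL PET/CT".
- PSA: "PSA does not decrease by ≥50% from baseline following RT (without concomitant ADT) up to 9 months following initiation of such treatment".

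On reporting, SAP 8.5.2.2 says: "A summary table will present the number and percent of subjects with either false negative or true negative outcomes for each central imaging reader". A listing of these subjects is also planned. The denominator of the percentage is not given.

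On the population, inclusion criterion 3 in Protocol 5.1 begins: "Suspected recurrence of prostate cancer based on rising PSA after definitive therapy on the basis of". Protocol 1.2 describes this PSA state as disease recurrence.

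**The concern.** A subject-level true negative says that the man had no recurrence and that the reader was right to call nothing. The truth standard in this plan was built for a different question, namely whether a lesion that a reader marked can be confirmed. It is collected only in locally positive men and is aimed at the locally suspected lesions. When it comes back negative, it speaks to those lesions and not to the whole man.

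The PSA route is the clearest case. For a positive call, non-response is at least relevant: the treated target did not account for the PSA. For a negative call it cannot be turned round into support, because a PSA that has not halved after radiotherapy suggests that disease may still be present.

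At stake is how one exploratory table is read. Someone who sees true negatives per reader, with a percentage, is likely to take them as men shown to be disease-free, and may treat the figure as a form of specificity or negative predictive value.

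**Working it through.** **1. The planning figures, reproduced.** Inputs from SAP 7.1 are an assumed CLR of 0.30, a lower 95% bound of 0.20, a positive-scan rate of 0.60 and a non-evaluable rate of 0.30.

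- Positive scans: 1.96² × 0.30 × 0.70 / (0.30 − 0.20)² = 80.67, so 81, as stated.
- Scans: 80.67 / 0.60 = 134.45 (stated as 134).
- Enrolled: 134 / 0.70 = 191.4, so 192, as stated.

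None of these uses a true-negative count.

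**2. What each negative route establishes.**

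| Route | What was found | What it leaves open |
|---|---|---|
| Histopathology | One sampled lesion is negative; Protocol 8.2.3 directs biopsy to a lesion amenable to it | Any lesion not sampled |
| Correlative imaging | All suspected lesions are negative. In a centrally negative man these can only be the local reader's lesions | Disease that conventional imaging cannot see. Protocol 1.2 says these methods have low sensitivity, and criterion 4 admits only men already negative or equivocal on them |
| PSA after RT | Less than a 50% fall up to 9 months | Disease elsewhere, resistant disease or a slow response |

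No row establishes absence of recurrence.

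**3. Histopathology with several lesions.** Assume, for illustration only, that each lesion is independently real with probability q between 0.3 and 0.7. After one negative biopsy among k lesions, the chance that at least one other is real is 1 − (1 − q)^(k−1).

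- k = 2: 0.30 to 0.70.
- k = 3: 1 − 0.7² = 0.51 to 1 − 0.3² = 0.91.

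**4. The PSA route against the protocol's own threshold.** A non-responder keeps more than half of his baseline PSA. Protocol 1.2 puts recurrence after prostatectomy at a confirmed PSA of at least 0.2 ng/mL.

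- Baseline 0.4: PSA stays above 0.5 × 0.4 = 0.20 ng/mL.
- Baseline 1.0: PSA stays above 0.50 ng/mL.
- Baseline 0.3: above 0.15 ng/mL, so the threshold is not necessarily exceeded.
- Baseline 0.2: above 0.10 ng/mL, likewise.

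From a baseline of 0.4 ng/mL upward, a post-prostatectomy non-responder therefore exceeds the recurrence threshold by definition. If a central reader called his scan negative, SAP 5.1.3 records a true negative.

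**5. What the label feeds into.**

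- CLR = TP / (TP + FP). Central negatives do not enter.
- True positive detection rate = TP / (TP + FP + TN + FN). Only the sum TN + FN enters, and SAP 5.1.3 allows for the split being unknown.
- The false-negative/true-negative table and listing in SAP 8.5.2.2 are the outputs that change.

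**6. Possible size.** The documents give no count. Suppose 81 locally positive men have truth data, a central reader calls 5% to 30% of them negative, and 30% to 70% of those have a positive truth standard. All these shares are assumptions.

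- Fewest: 81 × 0.05 ≈ 4 men; with 70% positive, 3 are false negatives and 1 is labelled true negative.
- Most: 81 × 0.30 ≈ 24 men; with 30% positive, 7 are false negatives and 17 are labelled true negative.

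This gives 1 to 17 men per reader across all three routes. Zero is also possible if local and central reads agree.

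**The case against.** The best defence is that a true negative is always relative to the stated reference. The same negative result makes a centrally positive man a false positive in the primary endpoint, so relabelling one side leaves one man a false positive for one reader and undetermined for another. That asymmetry is real but justified. A positive call makes a claim about a lesion, and failure to confirm it bears on that claim. A negative call, labelled at subject level, makes a claim about the whole man, which the same evidence does not test. At lesion level the central reader may well have been right not to call the lesion; the fault is in the subject-level label.

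Other points stand as limits:

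- Applying the SAP 5.1.1 definitions to centrally negative scans is a reasonable reading, but the text does not state it.
- PSA is the third-line source, needs radiotherapy without ADT started within 60 days of the scan, and is lost if data are missing at database lock. If the Table 4 rule on untreated lesions carries over, only men irradiated at every suspected lesion count. Few may reach this route.
- The planned listings let a reader trace the source of truth for each man.

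A reader might also infer more than the documents support:

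- *That men with proven recurrence are counted as correct negatives.* A positive truth standard makes a man a false negative. The evidence on the PSA route is biochemical, and non-response includes any fall short of 50%.
- *That a single unconfirmed lesion suffices on every route.* That is true of histopathology. Correlative imaging requires all suspected lesions to be negative.
- *That this table is the only view of what central readers miss.* SAP 8.5.6 compares each central reader with the local reader, SAP 8.5.4 gives detection rates for both, and the true positive detection rate keeps all negative scans in its denominator.
- *That the plan reports a negative predictive value or rewards cautious readers.* No such analysis or specificity is planned and the percentage has no stated denominator. A reader who calls fewer scans positive lowers his own detection rate and may add false negatives.

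**Conclusion.** The concern holds as a labelling error in an exploratory output. Followed as written, SAP 5.1.3 counts men as correctly negative on evidence that leaves their disease status undetermined and, for PSA non-responders, on evidence that points towards persisting disease. This rests on two things: reading a negative truth standard from SAP 5.1.1, and the protocol's own description of rising PSA as recurrence.

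The importance is low. No success criterion uses the label, and the primary result, the sample size and the true positive detection rate are untouched. The number of men cannot be derived from the documents.

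**What to change.** - **SAP 5.1.3:** keep *false negative* for a negative central read with a positive truth standard. Replace *true negative* with *central negative, locally suspected lesion not confirmed (disease status undetermined)*. State that the negative findings listed in 5.1.1 are the ones meant.
- **SAP 8.5.2.2:** report counts by truth-standard type (histopathology, correlative imaging, PSA after RT). Show PSA non-responders on a separate line that is not counted as true negative. Drop the true-negative percentage. Use the same labels in the listing.
- **True positive detection rate:** keep the sum of all negative scans in the denominator, so that its value does not change.

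The cost is a wording change and one relabelled table and listing, with no new data. The downside is that the trial no longer reports a true-negative count.
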